5.2.9. Pharmacokinetic/Pharmacodynamic Analyses

Not applicable.

5.2.10. Health Outcome/Quality of Life Analyses

The Insulin Treatment Satisfaction Questionnaire (ITSQ) will be completed at Weeks 4 (Visit 6), 12 (Visit 12) and 24 (Visit 18) or ED.

The following will describe the analyses details for ITSQ.

5.2.10.1. Insulin Treatment Satisfaction Questionnaire

The ITSQ is a validated instrument containing 22 items that assesses treatment satisfaction completed at weeks 4 (visit 6), 12 (visit 10), and 24 (visit 18) or early discontinuation for persons with diabetes who are taking insulin. Items are measured on a 7-point scale in which lower scores reflect better outcomes. In addition to an overall score, the items that make up the 5 domains of satisfaction are categorized as:

- Inconvenience of Regimen (IR - 5 items)
- Lifestyle Flexibility (LF - 3 items)

- Glycemic Control (GC - 3 items)
- Hypoglycemic Control (HC - 5 items)
- Insulin Delivery Device (DD - 6 items).

All individual patient raw domain scores will be calculated as the mean of the individual item scores in the domain. If an item score is missing for a patient and <20% of the items within the domain are missing for that patient, then the mean of the items in the domain will be imputed for the missing item score(s). Individual patient with equal or more than 20% missing items in a domain, the domain score will be set to missing.

The individual transformed domain scores are then calculated as follows: use the following formula to transform the raw domain scores on a scale from 0-100 where higher scores indicate better treatment satisfaction:

$$\text{Transformed domain score} = 100 * [(7 - \text{raw domain score}) / 6]$$

The individual raw and transformed overall scores are then calculated as follows: first, calculate the raw overall score as the mean of the raw domain scores for that patient. If any of the domain scores is missing, then set the raw overall score to missing. Then, use the following formula to transform the raw overall score on a scale from 0-100 where a higher score indicates better treatment satisfaction:

$$\text{Transformed overall score} = 100 * [(7 - \text{raw overall score}) / 6]$$

Only the transformed domain and overall scores will be analyzed using the MMRM model for the FAS population. The MMRM model will have treatment (LY2963016, Lantus®), entry use of insulin secretagogue (SU, meglitinide, neither), visit, and interaction between visit and treatment as fixed effects; the baseline HbA_{1c} value as covariate; and a random effect for patient.

5.2.11. Safety Analyses

5.2.11.1. Adverse Events

Analyses of adverse events will include all data collected during the course of the entire study including the follow up visit, regardless of IP use.

Adverse events will be listed by patient, system organ class, Medical Dictionary for Regulatory Activities® (MedDRA) preferred term, severity, and relationship to the study disease, drug, device, or procedure for all patients. Adverse events (including injection site reactions, allergic events, and neoplasms) will be summarized as TEAEs for the FAS. Treatment-emergent adverse events are defined as events that are newly reported after first study treatment following randomization or reported to have worsened in severity from baseline. The proportion of patients experiencing each TEAE will be presented by preferred term, system organ class (SOC), and treatment group. The proportion of patients experiencing each TEAE that is assessed as possibly related to the study disease, drug, device, or procedures will also be summarized. The number of patients and proportion will be presented and compared by treatment using Fisher's

exact test or Pearson's chi-square test for the FAS population. TEAE will be summarized by preferred term within SOC and by preferred term by decreasing frequency.

All SAEs will be listed by patient and summarized by treatment as counts and percentages. If a sufficient number of SAEs are reported, the proportion of patients with SAEs between treatment groups will be compared using Fisher's exact test. Similar analyses will be performed for discontinuations due to AEs.

Summary table of historical conditions and pre-existing condition will be listed by preferred term and ordered by decreasing order of the total group. Historical conditions are conditions that end prior to inform consent and preexisting conditions are conditions that are still ongoing at inform consent or the conditions that started after inform consent and before first does.

A listing of subjects discontinue IP or study due to adverse event including death will be presented.

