**Planned Duration of Treatment:**

Lead-in period: None

Treatment period: 24 weeks

Washout period: None

Observation period: 4 weeks

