subject	An individual who is or becomes a participant in clinical research, either as a recipient of the investigational product(s) or as a control. A subject may be either a healthy human or a patient.
suspected unexpected serious adverse reactions (SUSARs)	Suspected unexpected serious adverse reactions are serious events that are not listed in the Investigator's Brochure (IB) and that the investigator identifies as related to investigational product or procedure.
T2DM	type 2 diabetes mellitus
TEAR	treatment emergent antibody response
TEAE	Treatment-emergent adverse event: An untoward medical occurrence that emerges during a defined treatment period, having been absent pretreatment, or worsens relative to the pretreatment state, and does not necessarily have to have a causal relationship with this treatment.
U	unit(s)
ULN	upper limit of normal
WHO	World Health Organization

---

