#### **7.2.2.3.2. Office Visits (Visits 4, 6, 8, 10, 12, 14, 16, and Visit 18 or Early Discontinuation)**

The following activities occur during investigator site Visits 4, 6, 8, 10, 12, 14, 16, and Visit 18 or Early Discontinuation (ED):

- study diaries collected and reviewed for BG levels, episodes of hypoglycemia, insulin self-administration ([Section 7.2.2.2](#))
- distribute study diaries (not completed at ED)
- dispense study drug with prefilled pen injector (not completed at Visits 4, 8, 18, or ED)
- collect study drug at Visits 6, 10, 12, 14, 16, 18, and ED
- collection of blood sample for HbA1c assessment to determine efficacy of treatment values for each patient at Visits 6, 10, 12, 14, 16, 18 or ED

- blood sampling for chemistry and hematology at Visit 18 or ED
- transfer data from study diaries into eCRF (including previous day's insulin dose from last telephone visit)
- adjustment of insulin doses as needed during Visits 4, 6, 8, 10, 12, 14, and Visit 16 (not completed at Visits 18 or ED)
- previous day's insulin dose
- assessment of vital signs, body weight
- inquiries of AEs
- inquire about use of concomitant medications
- collection of blood sample to determine generation of anti-glargine antibodies at Visits 4, 6, 12, and Visit 18 (or ED)
- collection of serum samples for biomarker analysis during Visit 10 and Visit 18
- administer the ITSQ questionnaires during Visits 6, 12, and Visit 18 (or ED)
- dispense BG monitoring supplies as required

In addition to the daily BG monitoring, patients will be instructed to complete:

- 7-point SMBG profiles (described in Section 7.2.3) on 2 separate days in the 2-week period prior to Visits 4, 8, 12, and 18 (or at ED) (preferably most recent readings).
- 4-point SMBG values recorded (once before each meal and at bedtime) on 3 separate days before phone visits then transferred to the eCRF in succeeding office visit (preferably most recent readings).

Patients are instructed on a post-treatment insulin regimen which is at discretion of the investigator (at Visit 18 or ED).

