### 9.2. Materials and Supplies

Clinical trial materials will be labeled and should be handled and stored according to the respective country's regulatory requirements.

The reference therapy (Lantus®) used in this clinical trial is approved for use in each respective country.

Patients must continue to use their prestudy OAMs throughout the study (Section 9.8.1).

Patients on metformin must continue or discontinue the use of metformin based on Inclusion Criterion [4].

Patients randomized to LY2963016 will be provided with LY2963016 as a 100 U/mL solution for injection in a prefilled pen injector. Patients randomized to Lantus® will be provided with Lantus® as a 100 U/mL solution for injection in prefilled pen injector. In addition, a commercially available glucometer will be provided with the necessary supplies.

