## 9.6. Continued Access to Investigational Product

The Sponsor will not provide patients with ongoing supplies of study medication after they have completed the study treatment period because LY2963016 is experimental.

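### SAP 5.2.11.1 compares adverse events between arms only over the whole study, including about 4 weeks after study insulin stops; a treatment-period comparison is needed beside it

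*SAP*

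**What the plan says.** - **Window.** Under SAP 5.2.11.1, adverse event analyses will "include all data collected during the course of the entire study including the follow up visit, regardless of IP use".
- **TEAE rule.** The same section counts "events that are newly reported after first study treatment following randomization or reported to have worsened in severity from baseline". This has a start but no end. Protocol 12.2.9.3 uses the same definition.
- **Glossary.** Protocol Section 4 describes a TEAE as "An untoward medical occurrence that emerges during a defined treatment period", without giving dates for that period.
- **Comparisons.** SAP 5.2.11.1 tests TEAE proportions between arms in the full analysis set by Fisher's exact or chi-square test. SAP 5.2.11.1.1 and 5.2.11.1.2 compare allergic and injection-site events by arm and state no other window. Injection-site reaction is one of the safety measures named in the secondary objectives (SAP 4.2).
- **After treatment.** The synopsis gives "Treatment period: 24 weeks" and then a 4-week observation period. Protocol 7.2.2.3.2 leaves the insulin taken after Visit 18 or early discontinuation to the investigator. Protocol 9.6 adds: "The Sponsor will not provide patients with ongoing supplies of study medication", because LY2963016 is experimental. Visit 801, about 4 weeks later, collects adverse events, concomitant medications and the insulin dose if insulin continues. Early discontinuers attend it too (Protocol 7.2.2.4, Attachment 1).

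**The concern.** An event that starts in follow-up arises on whatever regimen the investigator chose, yet it is counted under the randomized arm. In a trial meant to show that two insulins are alike, person-time off both study products adds noise to the safety contrast and can pull it toward no difference. If the two arms have different insulin exposure in follow-up, it can also shift the contrast.

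Injection-site and allergic events are most exposed, because they depend on the product injected. No comparison limited to time on study insulin is planned, so a reader of the report could not tell whether the result depends on the follow-up weeks.

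**Working it through.** The documents give no event rate and no planned figure for the adverse event comparisons, so there is no sponsor figure to reproduce. From the sample-size section (SAP 5.1) I use only the 15% dropout rate and the arm sizes of 353 and 177. Event rates, hazard ratios and dropout timing below are assumptions.

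**1. Windows side by side**
- Adverse events (SAP 5.2.11.1): first study treatment through the follow-up visit.
- Exposure (SAP 5.2.11.6): first to last dose.
- Overall treatment-emergent antibody response, TEAR (SAP 5.2.11.4): the 24-week treatment period.

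The TEAR-by-adverse-event analysis in SAP 5.2.11.4 therefore crosses antibody status over 24 weeks with event incidence over about 28 weeks.

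**2. Share of observed time in follow-up**
- Completer: 4/28 = 14.3%.
- Patient stopping at Week 4: 4/8 = 50%.
- Mixed, with 85% completers and dropouts averaging 12 weeks on treatment (assumed): 4/(0.85 × 28 + 0.15 × 16) = 4/26.2 = 15.3%.

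**3. Dilution for rare events, both arms at the Lantus rate in follow-up (assumed)**

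Observed ratio = 0.847 × true ratio + 0.153.
- True 2.0: 1.694 + 0.153 = 1.85.
- True 1.5: 1.2705 + 0.153 = 1.42.

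**4. Cumulative incidence and power**

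Assume a constant weekly hazard h = −ln(1 − p)/24, a Lantus 24-week incidence p = 5% and an on-treatment hazard ratio of 2. Power = Φ[(difference − 1.96 × pooled SE)/unpooled SE], with 177 and 353 patients.

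| Window | Lantus | LY2963016 | Risk ratio | Power |
|---|---|---|---|---|
| 24 weeks | 5.0% | 1 − 0.95² = 9.75% | 1.95 | 46.6% |
| 28 weeks, equal follow-up hazard | 1 − 0.95^(28/24) = 5.81% | 1 − 0.95^(52/24) = 10.52% | 1.81 | 42.7% |
| 28 weeks, follow-up events in the Lantus arm only | 5.81% | 9.75% | 1.68 | 32.5% |

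For assumed incidences of 2% to 30% and hazard ratios of 1.5 to 3, equal follow-up hazards lower the risk ratio by about 5% to 10% and power by 0 to about 7 points. The Lantus-only case lowers the risk ratio by about 11% to 14%.

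**5. No true difference, unequal follow-up exposure (p = 5%)**
- Follow-up events in the Lantus arm only: 5.0/5.81 = 0.86.
- Follow-up events in the LY2963016 arm only: 5.81/5.0 = 1.16.

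These are limiting cases. They show that the bias can go either way.

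**The case against.** The case for leaving the plan alone has real strength.

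- **The window is prespecified and deliberate.** Counting events regardless of study-drug use fits analysis by randomized arm, and it keeps delayed reactions. Protocol 7.2.2.2.1.1 itself tells patients to watch for delayed hypersensitivity. This stands, and it is why the all-study analysis should not be replaced.
- **The SAP does not depart from the protocol's analysis section.** A reader might infer a conflict from the glossary, but Protocol 12.2.9.3 and the SAP agree. Only Section 4 differs, and it gives no dates.
- **The post-study asymmetry is not established.** A reader might infer that Lantus patients stay on Lantus while LY2963016 patients must switch. Protocol 9.6 ends sponsor supply for both arms, Protocol 9.2 says only that Lantus is approved, and no section says who continues, switches or stops insulin.
- **Nothing confirmatory depends on these tests.** They have no margin or success rule, and the SAP makes no multiplicity adjustment for them.
- **Part is already covered.** Antibody analyses are confined to 24 weeks, and hypoglycemia is also reported for the titration and maintenance periods. Related TEAEs are summarized separately, which limits misattribution. But the main TEAE, allergic and injection-site comparisons are not restricted to related events, so the gap remains for them.

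**Conclusion.** The point holds as a missing analysis, not as an error in the one that is planned. The only between-arm TEAE comparison mixes time on study insulin with about 4 weeks off it, which is 14.3% of a completer's time.

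Under equal follow-up rates a true ratio of 2.0 appears as about 1.85, and in the worked 5% example power falls by about 4 points. Larger shifts need sharply unequal follow-up exposure, for which the documents give no figures. A reader might infer that the design always favours a finding of no difference; the documents do not support that, because the direction depends on what patients take after Visit 18. The effect is probably modest. It still deserves correction because injection-site reaction is a named secondary safety measure and the remedy uses data already collected.

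**What to change.** Keep the all-study TEAE analysis and make these changes:

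- **Treatment-period comparison.** In SAP 5.2.11.1, 5.2.11.1.1, 5.2.11.1.2 and the TEAR-by-adverse-event analysis in 5.2.11.4, add a between-arm comparison from first dose to last dose of study insulin plus a short lag. State the lag and its reason before database lock. Use the actual last-dose date, as the exposure calculation does, because it can precede Visit 18 or early discontinuation: Protocol 8.3.3 requires discontinuation only after more than 14 consecutive days off study medication.
- **Follow-up table.** Show events after that window by randomized arm, with the insulin taken as recorded at Visit 801.
- **Serious events.** Keep all SAEs and deaths in the all-study tables and listings.
- **Definitions.** Align Protocol Section 4, Protocol 12.2.9.3 and SAP 5.2.11.1, and state the end of each window.

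The cost is a few extra tables and one date rule, with no new visit or assessment. The treatment-period comparison will omit some late-onset events; these stay in the all-study analysis.

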5.2.11.1.1. Special Topic Assessment of Allergic Events

The special topic assessment of allergic events will be performed by an initial blinded review of preferred terms (PTs) by SOC in order to identify all possible cases of allergic events, followed by a comparison between treatment arms. The goal of the initial blinded review, which will be carried out by the safety physician, is to identify all reported allergic reactions. As an initial reference for this blinded review, Lilly will consider the list of PTs shown in [Appendix 1](#). Justification in including or excluding events based on medical judgment and other supportive information will be provided when applicable. All allergic events will be listed by patient and summarized by treatment as counts and percentages. The proportion of patients with allergic reactions between treatment groups will be compared using Fisher's exact test or Pearson's chi-square test for the FAS.

5.2.11.1.2. Assessment of Injection Site Adverse Events

Whenever an injection site adverse event occurs, there is an evaluation of the pain, pruritus, and rash associated with the injection as well as of the characteristics of the injection site (abscess, nodule, lipatrophy, lipohypertrophy, or induration). The proportion of patients experiencing treatment emergent injection site adverse events will be summarized and analyzed by treatment group. Additional analyses will be done as deemed appropriate.

5.2.11.2. Hypoglycemic Events

A **hypoglycemic episode** is that at any time a patient feels as he/she is experiencing a sign or symptom that is associated with hypoglycemia or has a BG level of ≤ 70 mg/dL (≤ 3.9 mmol/L), even if it was not associated with signs, symptoms, or treatment.

Severe hypoglycemia: an event requiring assistance of another person to actively administer carbohydrates or glucagon or take other corrective actions. Plasma glucose concentrations may not be available during an event, but neurologic recovery following the return of plasma glucose to normal levels is considered sufficient evidence that the event was induced by low plasma glucose concentration.

Nocturnal hypoglycemia: any total hypoglycemic event that occurs after bedtime and prior to the first meal upon waking (eg, breakfast).

Documented symptomatic hypoglycemia: an event during which typical symptoms of hypoglycemia are accompanied by a measured plasma glucose concentration ≤ 70 mg/dL (≤ 3.9 mmol/L).

Asymptomatic hypoglycemia: an event not accompanied by typical symptoms of hypoglycemia but with a measured plasma glucose concentration ≤ 70 mg/dL (≤ 3.9 mmol/L).

Probable symptomatic hypoglycemia: an event during which symptoms typical of hypoglycemia are not accompanied by a plasma glucose determination but that was presumably caused by a plasma glucose concentration ≤ 70 mg/dL (≤ 3.9 mmol/L).

Besides the hypoglycemic categories listed above, total hypoglycemic event will be defined as follows:

Total hypoglycemic event: any event which is either documented symptomatic hypoglycemia, asymptomatic hypoglycemia, probable symptomatic hypoglycemia or severe hypoglycemia.

For each category of hypoglycemia event, the incidence, the number of hypoglycemic events per patient, the rate of hypoglycemic events per year (that is, the number of hypoglycemic episodes per patient per patient year [365.25 days]) will be calculated. These measures will be summarized at baseline, titration, maintenance, and overall study periods and at endpoint.

The proportion of patients with at least 1 hypoglycemic event (total, severe, nocturnal, and others) or incidence during the study will be summarized (counts and percentages) and analyzed using Fisher's exact test or the Pearson's chi-square test for the FAS population.

Logistic regression will be used as a sensitivity analysis of the incidence of hypoglycemia. The model will have presence or absence of hypoglycemia as the dependent or response variable and treatment, baseline HbA_{1c}, and entry use of insulin scretagogue (SU, meglitinide, neither) as the independent terms in the model.

The rate of hypoglycemic episodes per year (total, severe, nocturnal, and others) will be analyzed at baseline, titration, maintenance, and overall study periods and at endpoint using the Wilcoxon test. In addition, the hypoglycemia rates will also be analyzed using a negative binomial model for the FAS population with terms for treatment, baseline HbA_{1c}, and entry use of insulin scretagogue (SU, meglitinide, neither).

In addition, the total number of patients with at least 1 hypoglycemic episode divided by the total extent of exposure in patient-years will be calculated for the overall study period and summarized descriptively for each treatment group for total, severe, nocturnal, documented symptomatic, asymptomatic hypoglycemia and probable symptomatic hypoglycemia. Individual patient listing of hypoglycemic events by visit will be presented for the FAS population.

All the above analysis will be repeated with the threshold of **Clinically significant hypoglycemia:** < 54 mg/dL (3.0 mmol/L) for hypoglycemia categories of total hypoglycemia,

nocturnal hypoglycemia, documented symptomatic hypoglycemia and asymptomatic hypoglycemia.

